Section 4.2.11.3 Analysis of CCI	21Dec2023	Added text for baseline terms to be used in the MMRM model	Yes	Provided clarity on how to conduct the MMRM and updated the terms to be included in the model to align with other Koselugo studies
Section 4.2.12.3 Analysis of CCI	21Dec2023	Added text for baseline terms to be used in the MMRM model	Yes	Provided clarity on how to conduct the MMRM and updated the terms to be included in the model to align with other Koselugo studies
Section 4.6.3.1 Definitions and Derivations	21Dec2023	Corrected link under Table 15	Yes	Correction of table link error
Section 4.4.2.1 Plasma Concentrations	10Jan2024	Added text for on-treatment BSA groups	Yes	Provided clarity on which BSA groups should be used for the PK data presentations
Section 4.4.2.2 Pharmacokinetic Parameters	10Jan2024	Added text for on-treatment BSA groups	Yes	Provided clarity on which BSA groups should be used for the PK data presentations
Section 4.4.2.3 PK Graphical Presentation	10Jan2024	Added text for on-treatment BSA groups	Yes	Provided clarity on which BSA groups should be used for the PK data presentations
Section 4.6.6.2 Presentation	10Jan2024	Updated text 'weight/height' to 'BSA' for individual plots. Added text for inclusion of BSA group in listings.	Yes	Added BSA group in listings, for clarity on reporting. Individual plots of BSA over time more meaningful than weight/height plots over time.
Writing and formatting QC	30Jan2024	Writing and formatting QC Checks by Synchrogenix	N/A	As per company standards
Section 1	29Apr2024	Updated CSP version	N/A	New version available
Section 1.1	29Apr2024	Minor changes in the study design description, including removal of minimum sample size of xx for the Japanese cohort	No	To improve overall readability and to reflect early termination of recruitment with n= xx patients

CATEGORY Change refers to:	Date	Description of change	In line with CSP?	Rationale
----------------------------------	------	-----------------------	----------------------	-----------

Section 3.1	29Apr2024	Removed footnote “If there are any major variable changes in the database after the DCO, the outputs will be repeated at DCO2 and/or DCO3 (depending on the timing of the updates).	N/A	This will only occur in case of data issues found in the DCO1 CDL but we should not plan for it.
Section 3.2.2	29Apr2024	Clarification that IPDs affecting the PK may lead to the exclusion of some data points and not to the overall patient exclusion.	N/A	Clarification on the PK analysis set
Section 3.3.6	29Apr2024	Added sentence “If the imputed end date is after the date of study discontinuation, then the end date will instead be taken as the date of study discontinuation.”	N/A	To follow AZ Standards
Section 3.3.9	29Apr2024	Added sentence “Except for the palatability test where if the subject is not on treatment or if the subject transitioned to capsules the COA is not expected.	N/A	To better clarify an exception
Section 3.3.10	29Apr2024	Clarification on how to calculate Expected number of entries and compliance by week	N/A	Better
Section 3.4	29Apr2024	Section of Sample Size Determination included.	N/A	Provided detailed and accurate information about Sample Size Determination.
Section 4.1.1	29Apr2024	Added transition to capsule formulation to be presented as a new disposition	N/A	Required as per study design
Section 4.1.4.1 Definitions and Derivations	29Apr2024	Derived age calculated with Date Of Birth will be used instead of age collected in the eCRF.	N/A	Provided more accurate value for age, adding a decimal position to the age value.
Section 4.1.6.2	29Apr2024	Added presence of non-target PN, overall morbidity type and number of morbidities	N/A	Collected on CRF
Section 4.1.7	29Apr2024	Added last version of dictionaries, updated AstraZeneca Drug Dictionary to WHOdRUG Dictionary	N/A	As per latest coding standards

Section 4.2	29Apr2024	Added clarification that CCI [REDACTED] analyses	N/A	Clarification for the CSP analysis expectations
-------------	-----------	---	-----	---

CATEGORY Change refers to:	Date	Description of change	In line with CSP?	Rationale
		are not in scope of CSP		
Section 4.4.1.1 and Section 4.2.1.2	29Apr2024	Removed sentence around the interpretability of the primary and supplementary analysis	N/A	Out of scope for SAP
Section 4.2.3	29Apr2024	Detailed information about Derivation and Analysis of Palatability	N/A	Provided detailed and accurately information about Analysis of Palatability.
Section 4.2.5.4 and Section 4.2.5.6	29Apr2024	Updated Table with Overall Visit Response and with BOR categories	N/A	It was not correct
Section 4.2.5.7	29Apr2024	Added that ORR will be presented for the totals and not only by cohort	N/A	It was missing but needed for the data interpretation
Section 4..2.10.4	29Apr2024	Clarification that MMRM has cohort as fixed factor with estimates on the on the cohort-by-scheduled visit interaction and model not run by cohort	N/A	Clarification on modelling
Section 4.3 Pharmacodynamic Endpoint(s)	29Apr2024	PD analysis will not be performed in CSR.	N/A	PD data were not collected.
Section 4.4.1	29Apr2024	Added derivation of dose by BSA normalised (DBN)	N/A	Requested by PK scientist to help data interpretation in CSR
Section 4.4.2.1 Plasma Concentrations Section 4.4.2.2 Plasma parameters	29Apr2024	Remove cohorts and show the table only for the total by BSA.	Yes	Due to the most of the BSA groups within each cohort have less than 3 participants, PK analysis by BSA groups will be only undertaken in the total global.

Section 4.6.1 Exposure and treatment compliance	29Apr2024	Update text for Duration of exposure calculation adding date of DCO. Transition to capsule formulation information will be listed in the exposure listing.	N/A	Provide clarity and consistency in the Duration of exposure calculation. Transition to capsule formulation information will be listed in the exposure listing.
Section 4.6.2 Adverse Event	29Apr2024	Added granule formulation flag to the AEs listings.	Yes	Provided detailed information about the formulation (granule or

CATEGORY Change refers to:	Date	Description of change	In line with CSP?	Rationale
		Added table for AESI		capsule) when the AE starts. Provided terms to be mapped as AESI
Section 4.6.12 Physical Examination Including CCI	29Apr2024	Remove summary tables for Physical Examination	Yes	Not necessary, data for Physical Examination are available in listings section. Besides any abnormal or significant event will be collected in AEs section.

1 INTRODUCTION

The purpose of this document is to give details for the statistical analysis of study D1346C00004 supporting the CSR. The reader is referred to the CSP and the CRF for details of study conduct and data collection. This SAP is based on Amendment 4 of the CSP (Version 5.0) dated 15 March 2024.

If the SRC determines that the selumetinib AUC0-12 and safety are within the acceptable criteria, dosing of additional participants into Cohort 1 will continue, and dosing in the dose-finding phase for Cohort 2 will commence.

If the SRC thinks that the selumetinib AUC0-12 and safety are not within the acceptable criteria, dose adjustments will be made. Additional participants will be dosed in Cohort 1 in order to have an additional 3 evaluable participants. The dose-finding phase will continue to be assessed in this way until the granule formulation dose schema is identified and recommended for Cohort 1.

Once the granule formulation dose schema is identified for Cohort 1, dosing in Cohort 2 will commence in order to have 3 evaluable participants in Cohort 2 in the dose-finding phase. After completion of at least one cycle of dosing in the first 3 evaluable participants, the SRC will evaluate the PK, safety, and tolerability of the granule formulation in this dose schema. The same process described for Cohort 1 will be adopted for Cohort 2 in the dosefinding phase. The dose-finding phase will continue to be assessed in this way until the granule formulation dose schema is identified and recommended for Cohort 2.

Additional SRC reviews will be held for each of the cohorts following at least one cycle of dosing in approximately 6 evaluable participants and again in approximately CC evaluable participants. The SRC will evaluate the PK, safety, and tolerability of the granule formulation for that dose schema. The Japan Cohort will not participate in the dose-finding phase. Further information will be provided in the SRC charter.

At enrolment, participants must have a BSA within the range of 0.40 to 1.09 m²; once participants attain a BSA between 1.10 and 1.29 m², they will be encouraged to transition to the capsule formulation, if feasible; however, all participants must remain on the granule formulation until after they have completed their third cycle of treatment. Upon transition to the capsule formulation, PK sampling should be performed on Day 7 (range of Days 4 to 14) as long as the participant has received 3 consecutive days of twice daily dosing with capsule formulation immediately prior to the PK day (see CSP Section 8.5.1.1 for more details).

2 CHANGES TO PROTOCOL PLANNED ANALYSES

Not applicable.

3 DATA ANALYSIS CONSIDERATIONS

Summary statistics will be presented as per the AstraZeneca Corporate CSRHLD Reporting Standards to ensure consistency and alignment across AstraZeneca clinical studies.

3.1 Timing of Analyses

There are 3 planned DCOs for this study.

1 Pharmacokinetic, dose-finding, and primary safety analysis (DCO1): DCO1 will occur after all participants have had the opportunity to complete 3 cycles of treatment. This primary analysis will confirm the recommended granule formulation dose schema and assess the PK, safety/tolerability, and palatability. The timing of DCO1 may be different for the Global Cohorts (Cohorts 1 and 2) from the Japan Cohort based on their date of Last Subject In.

2 Safety and efficacy of the granule formulation (DCO2):

DCO2 will occur after all participants in the study (Global and Japan Cohorts) have had the opportunity to complete 25 cycles (or terminated selumetinib); this analysis will provide additional PK and safety/tolerability data, as well as palatability and efficacy data.

3 Long term safety follow-up for participants until they reach the age of 5 years or commence an alternative systemic NF1-PN treatment, whichever is the earlier (Final analysis and DCO3):

DCO3 and final analysis will occur when all participants in the study (Global and Japan Cohorts) have had the opportunity to complete their last assessment in the study, including the safety follow-up for participants aged < 5 years. All of the safety/tolerability analyses will be updated with the data captured after DCO2 (safety of the granule formulation).

The different analyses planned for the DCOs are provided in [Table 1](#).

Table 1 Summary of Outcome Variables and Timing of Analyses

Outcome variable	Timing of analyses
Study population/demographic data	
Outcome variable	Timing of analyses
Disposition	DCO1, DCO2, and DCO3

Analysis sets	DCO1
Demographic characteristics	DCO1
Baseline and disease characteristics	DCO1
Important protocol deviations	DCO1, DCO2, and DCO3
Medical history	DCO1
Prior and concomitant medication	DCO1, DCO2, and DCO3
Efficacy data	
ORR CCI	DCO2
Clinical outcome assessment data	
Parent-reported palatability	DCO1 and DCO2
CCI	DCO2
CCI	DCO2
CCI	DCO2
CCI	DCO2
Outcome Variable	Timing of analyses
CCI	DCO2
CCI	DCO2
Safety Data	
Exposure and treatment compliance	DCO1, DCO2, and DCO3
Adverse events	DCO1, DCO2, and DCO3
Laboratory measurements	DCO1, DCO2, and DCO3
Vital signs (including height, weight, and BSA)	DCO1, DCO2, and DCO3
ECG and ECHO	DCO1, DCO2, and DCO3
Ophthalmologic assessments	DCO1, DCO2, and DCO3
Knee (or wrist) MRI/X-ray	DCO1, DCO2, and DCO3
Performance status	DCO1, DCO2, and DCO3
Physical examination	DCO1, DCO2, and DCO3
CCI	DCO2 and DCO3
PK data	

Selumetinib and N-desmethyl selumetinib plasma concentration data and PK parameters	DCO1 and DCO2
Pharmacodynamic data	
pERK inhibition	DCO1 ^a and DCO2

^a Only if all Pharmacodynamic data are already available at DCO1. If available at DCO1, Pharmacodynamic data will not be presented at DCO2.

CC1 [REDACTED] CCI [REDACTED]; BSA, body surface area; CCI [REDACTED] CCI [REDACTED]; DCO, data cut-off; CCI [REDACTED] CCI [REDACTED]; ECG electrocardiogram; ECHO, echocardiogram; CCI [REDACTED] [REDACTED]; CCI [REDACTED] [REDACTED]; MRI, magnetic resonance imaging; ORR, objective response rate; PD, pharmacodynamic; CCI [REDACTED] CCI [REDACTED]; pERK, phosphorylated extracellular signal regulated kinase; CCI [REDACTED] [REDACTED]; PK, pharmacokinetic; CCI [REDACTED] [REDACTED].

3.2 Analysis Populations

3.2.1 Enrolled

All participants who signed the informed consent form (ICF) are considered enrolled.

3.2.2 Pharmacokinetic Analysis Set

All participants who received at least one dose of selumetinib and who have at least one post-dose quantifiable plasma concentration with no IPDs.

IPDs here refer to documented important clinical protocol deviations potentially affecting PK analysis. In order to categorise the important clinical protocol deviations, prior to database lock, a data review meeting will be conducted to assess each participant's evaluability for the PK analysis set. The data review will take into account the IPDs, compliance, AEs, concomitant medications, and PK sample timing and quality, which may have a potential effect on the PK analysis of each datapoint. Any issues thought to impact the PK data may result in the exclusion of impacted concentration data from the PK analysis and/or exclusion of impacted concentrations and parameters from the PK summaries rather than exclusion from the PK analysis set. The reason(s) for exclusion will be documented by the PK Scientist in the Non-compartmental PK Analysis (NCA) Notes and discussed in the CSR.

The available concentration and parameter data for any participants excluded from the PK data summaries will be listed and flagged with the reason for exclusion. The concentration data for participants excluded from the PK summaries will be presented in the individual figures of concentration versus time plots.

Note: The PK data for the Japan Cohort will be summarised separately from the PK data for the Global Cohorts.

3.2.3 Safety Analysis Set

All participants who received at least one dose of selumetinib.

3.2.4 Summary of outcome variables and analysis sets

The analysis sets for each outcome variable are provided in [Table 2](#). For some outcome variables, the analysis set will use a further subset (eg, participants who are evaluable for the analysis of **CCI** are those who **CCI** analysis), which are described in detail in the endpoint analysis sections in [Section 4.2](#).

Table 2 Summary of Outcome Variables and Analysis Sets

Outcome variable	Analysis set
Study population/demographic data	
Disposition	All Enrolled
Demography characteristics	Safety and PK
Baseline and disease characteristics	Safety
Important protocol deviations	Safety
Medical history	Safety
Prior and concomitant medication	Safety
Efficacy data	
CCI	Safety
Clinical outcome assessment data	
Parent-reported palatability	Safety
CCI	Safety
Safety data	
Outcome variable	Analysis set
Exposure and treatment compliance	Safety
Adverse events	Safety

Laboratory measurements	Safety
Vital signs (including height, weight, and BSA)	Safety
ECG and ECHO	Safety
Ophthalmologic assessments	Safety
Knee (or wrist) MRI/X-ray	Safety
Performance status	Safety
Physical examination	Safety
CCI CCI	Safety
PK data	
Selumetinib and N-desmethyl selumetinib plasma concentration data and PK parameters	PK
Pharmacodynamic data	
pERK inhibition	Safety

CCI CCI

surface area; CCI

ECHO, echocardiogram; CCI CCI

CCI

; MRI, magnetic resonance imaging; ORR, objective response

rate; CCI CCI; pERK, phosphorylated extracellular signal regulated

kinase; CCI

BSA, body

; ECG, electrocardiogram;

PK, pharmacokinetic; CCI

3.3 General Considerations

The below mentioned general principles will be followed throughout the study:

- Descriptive statistics will be used for all variables, as appropriate. Continuous variables will be summarised by the number of observations, mean, standard deviation, minimum, Q1, median, Q3, and maximum. For log-transformed data, it is more appropriate to present geometric mean, geometric coefficient of variation, median, minimum, and maximum. Categorical variables will be summarised by frequency counts and percentages for each category.
- For continuous data, the minimum and maximum will be displayed with the same accuracy as the original data. For laboratory data where decimal precision is provided, the maximum and minimum will be displayed to the standard decimal precision. The mean, median, Q1, and Q3 will be rounded to one additional decimal place compared to the minimum/maximum. The standard

deviation will be rounded to 2 additional decimal places compared to the minimum/maximum.

- For categorical data, percentages will be rounded to one decimal place with the exception of **CCI**, which is presented as a whole number. For 0 results, the percentages will not be included, and only 0 will be presented as a result of the categorical variable.
- Unless otherwise stated, percentages will be calculated out of the population total for the corresponding treatment group.
- Descriptive summaries for all endpoints will be based on the planned visit schedule unless otherwise stated.
- SAS® version 9.4 or above will be used for all analyses.

3.3.1 Baseline and Change from Baseline Definition

Baseline is defined as the last non-missing value obtained prior to the first dose of selumetinib.

Assessments on the day of the first dose where time is not captured will be considered prior to the first dose if such procedures are required by the CSP to be conducted before the first dose.

If two or more measures are recorded on the same day with no time (or on the same day with the same time/timepoint), then the average will be used as the baseline. For nonnumeric laboratory tests (ie, some of the urinalysis parameters) where taking an average is not possible, then the best value would be taken as baseline as this is the most conservative.

In all summaries, the change from baseline variables will be calculated as the posttreatment value -minus the value at baseline.

3.3.2 Study day

Study day is calculated in relation to the date of first dose of study intervention.

- Study Day 1 is defined as the day of first dose of study intervention.
- Study days prior to the date of first dose of study intervention are defined as the date of assessment – date of first dose of study intervention.
- Study days after the first dose of study intervention are defined as: (date of assessment – date of first dose of study intervention) + 1.

3.3.3 On-Treatment MRI

On-treatment MRI data will be defined as MRI data after the date of first dose of study intervention until the study intervention discontinuation date, DCO, or last day of Cycle 25, whichever occurs first.

3.3.4 Visit Window for safety and clinical outcome assessments

Visit windows will be defined for any presentations of safety and COAs that summarise values by visit. The following conventions will be applied:

- The time windows should be exhaustive so that data recorded at any timepoint have the potential to be summarised. Inclusion within the time window should be based on the actual date and not the intended date of the visit.
- All unscheduled visit data should have the potential to be included in the summaries.
- The window for the visits following baseline will be constructed in such a way that the upper limit of the interval falls halfway between the target days of the current and the next scheduled visit (the lower limit of the first post-baseline visit will be Day 2). If an even number of days exists between two consecutive visits, then the upper limit will be taken as the midpoint value minus 1 day. For example, the visit windows for vital signs data (with 2 weeks between scheduled assessments for Cycle 1 and 4 weeks for Cycle 2 onwards) are as follows:
 - Cycle 1 Day 15, visit window Days 2 to 21 –
 - Cycle 2 Day 1, visit window Days 22 to 42 –
 - Cycle 3 Day 1, visit window Days 43 to 70 –
 - Cycle 4 Day 1, visit window Days 71 to 98 –
 - etc.
- For summaries showing the maximum or minimum values, the maximum/minimum value recorded on treatment will be used (regardless of where it falls in an interval).
- Listings display all values contributing to a time point for a participant.
- For visit-based summaries, if there is more than one value per participant within a time window, then the closest value to the scheduled visit date will be summarised, or the earlier, in the event that the values are equidistant from the nominal visit date. The listings should highlight the value for the participant who contributed to the summary table, wherever feasible.

Note: In summaries of extreme values, all post-baseline values collected are used including those collected at unscheduled visits regardless of whether or not the value is close to the scheduled visit date.

3.3.5 Handling of Unscheduled Visits

Unscheduled visits are included in the method of assigning data to scheduled visits described in the rules in Section 3.3.4 above. Unscheduled visits are not included as separate visits in the summary tables.

For summaries at the participant level, such as of extreme values, all post-baseline values collected are used to derive a participant-level statistic including those collected at unscheduled visits and regardless of whether they appear in the corresponding visit-based summary.

3.3.6 Missing Data

In general, other than for partial dates, missing data will not be imputed and will be treated as missing unless specifically described in an analysis section. However, safety assessment values of the form of “ $< x$ ” (ie, below the LLOQ) or “ $> x$ ” (ie, above the upper limit of quantification) will be imputed as “ x ” in the calculation of summary statistics but displayed as “ $< x$ ” or “ $> x$ ” in the listings.

3.3.6.1 Missing Adverse event or concomitant medication dates

For missing AE/concomitant medication start dates, the following will be applied:

- Missing day: Impute the 1st of the month unless the month and year are the same as the month and year of the first dose of study intervention then impute first dose date.
- Missing day and month: Impute 1st of January unless the year is the same as in the first dose date, then impute first dose date.
- Completely missing: Impute the first dose date unless the end date suggests it could have started prior to this, in which case impute the 1st of January of the same year as the end date.

An imputed start date of an AE must be prior to the end date of the AE.

For missing AE/concomitant medication end dates, the following will be applied:

- Missing day: Impute the last day of the month unless the month is the same as the month of the last dose of study intervention then impute last dose date.
- Missing day and month: Impute 31st of December unless the year is the same as in the last dose date then impute last dose date.

- Completely missing: Assume that the AE is still ongoing (ie, do not impute a date). The imputation of dates for AEs and concomitant medications is used to determine if an AE is treatment emergent and whether a medication is concomitant. Flags are retained in the database indicating where any programmatic imputation has been applied, and in such cases, any durations are not calculated. If the imputed end date is after the date of study discontinuation then the end date will instead be taken as the date of study discontinuation

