4.1.8 Prior and Concomitant Medications and Procedures

4.1.8.1 Definitions and Derivations

Medications received prior to, concomitantly, or post-treatment are coded using the AstraZeneca Drug Dictionary ATC Classification codes.

For the purpose of inclusion in prior and/or concomitant medication or therapy summaries, incomplete medication start and stop dates are imputed as detailed in Section [3.3.6.1](#).

Prior, concomitant, and post-treatment medications and procedures are defined based on imputed start and stop dates as follows:

- Prior medications and procedures are those taken prior to study intervention with a stop date prior to the first dose of study intervention.

- Concomitant medications and procedures are those with a stop date on or after the first dose date of study intervention (and could have started prior to or during treatment).
- Post-treatment medications and procedures are those with a start date after the last dose date of study intervention.

Missing coding terms are listed and summarised as “Not coded”.

Procedures will be coded using the MedDRA (26.1 version or higher).

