4.1.8.2 Presentation

The following summary tables of the number and percentage of participants by ATC code and ATC text will be produced:

- Summary of prior medications
- Summary of allowed concomitant medications
- Summary of disallowed concomitant medications
- Summary of post-treatment medications

All concomitant medications will be listed.

Medication data will be presented for all participants in the safety analysis set. Procedures will not be summarised but will be listed. The individual participant data for subsequent PN therapy will also be listed.

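### The SAP's rule for an end date with a missing day matches the last dose on month but not year, so some medications stopped before treatment would be classed as concomitant

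*SAP*

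**What the plan says.** SAP 3.3.6.1 sets separate rules for partial start and end dates of adverse events and concomitant medications.

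- **Start date, day missing:** the first of the month, "unless the month and year are the same as the month and year of the first dose of study intervention", in which case the first dose date.
- **End date, day missing:** "Impute the last day of the month unless the month is the same as the month of the last dose of study intervention", in which case the last dose date.
- **End date, day and month missing:** 31 December, unless the year is that of the last dose, in which case the last dose date.

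The section states that the imputation "is used to determine if an AE is treatment emergent and whether a medication is concomitant". Its only cap on an imputed end date applies as follows: "If the imputed end date is after the date of study discontinuation", the discontinuation date is used instead.

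SAP 4.1.8.1 applies these imputed dates to the medication summaries. A drug is prior if its stop date is before first dose. For the other class, "Concomitant medications and procedures are those with a stop date on or after the first dose date of study intervention". SAP 4.1.8.2 lists separate tables for prior, allowed concomitant and disallowed concomitant medications, the last titled "Summary of disallowed concomitant medications".

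**The concern.** The missing-day end-date bullet is the only one of these three comparisons that leaves out the year. A stop date recorded with a known month and year can therefore have its year overwritten by the year of the last dose.

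A stop before first dose is what separates a prior medication from a concomitant one, so the overwritten year changes the class. Protocol 6.5 records medications from screening onward. Exclusion criterion 17 and Table 9 of the protocol require certain CYP inhibitors and inducers to be stopped at least 14 days or 5 half-lives before dosing, whichever is longer. Stop dates shortly before first dose are therefore expected, and a washout done as the protocol asks could be tabulated as use during treatment.

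**Working it through.** The plan gives no figure to reproduce. The check applies the rule as written, and again with the year added, to concrete dates.

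**Inputs**

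- Rule and classification: SAP 3.3.6.1 and 4.1.8.1, as above.
- Treatment length: 25 cycles (protocol 1.1) of 28 days = 700 days.
- Screening window: days -28 to -1 (protocol 1.3 and 6.3).
- Assumptions: last dose on day 700, that is first dose + 699 days; stop days spread evenly over the screening window; first-dose dates covering every day of 2022 to 2024 (1,096 dates).

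**Rules compared**

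- As written: stop = last dose date if month(stop) = month(last dose); otherwise month end.
- With year: stop = last dose date if month and year both match; otherwise month end.
- Class: prior if stop < first dose; otherwise concomitant.

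**Worked dates** (UN = day unknown)

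| First dose | Last dose | Recorded stop | As written | With year |
|---|---|---|---|---|
| 15-Feb-2023 | 14-Jan-2025 (day 700) | UN-Jan-2023 | 14-Jan-2025, concomitant | 31-Jan-2023, prior |
| 15-Feb-2023 | 14-Jan-2025 (day 700) | UN-Dec-2022 | 31-Dec-2022, prior | 31-Dec-2022, prior |
| 10-Jun-2023 | 15-Mar-2024 | UN-Mar-2024 | 15-Mar-2024, concomitant | 15-Mar-2024, concomitant |

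In the first row the stop date moves 714 days later (31-Jan-2023 to 14-Jan-2025). A study discontinuation date of, say, 13-Feb-2025 would not correct it, because the cap normally falls on or after the last dose. The third row shows that adding the year leaves a true stop in the last-dose month unchanged.

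**How often the months coincide at day 700**

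Two years is 730 or 731 days, so first dose + 699 days falls 31 or 32 days before the second anniversary of first dose. That is normally the calendar month before the first-dose month.

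- Over the 1,096 first-dose dates, the last-dose month equals the month before first dose for 1,052: 1,052 / 1,096 = 96%. The 44 exceptions all have a first dose in the first four days of a month.
- Screening-window stop days in total: 1,096 × 28 = 30,688. Of these, 14,616 fall in a month before the first-dose month. The other 16,072 fall in the first-dose month itself, where month-end imputation makes them concomitant whether or not the year is compared.
- Of the 14,616, the rule as written turns 13,404 from prior to concomitant: 13,404 / 14,616 = 92%. As a share of all screening-window stop days, 13,404 / 30,688 = 44%.

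**Other last-dose dates**

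If the last-dose month is unrelated to the stop month, the chance of a match is 1/12 = 8.3%. A child still on treatment at a data cut-off has no final last dose to match, so the problem does not arise for that child.

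**The case against.** The best defence is that the bullet concerns a missing day, and that the month of the last dose naturally means one particular month in one particular year. Overwriting a recorded year is replacement, not imputation, and the next end-date bullet compares the year, so the intent is clear. That is a fair reading of intent, and a careful programmer may code it so. But the start-date bullet in the same section spells out both month and year, so coding the end-date bullet literally is foreseeable.

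It is also fair that the reach is limited. Only records with month and year known, day missing and a matching month are affected. Imputations are flagged, and durations are not calculated from imputed dates. The medication tables count participants by ATC code, not length of use.

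Several stronger inferences are tempting, and the documents do not support them:

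- **A long look-back or a per-child risk.** Protocol 6.5 asks for medication being received from screening onward, so stops years before dosing are not the stated target. A child's records also share one last-dose month, so they cannot be treated as independent 1-in-12 chances.
- **Washed-out MEK inhibitors appearing as on-study use.** Prior PN therapy is summarised separately (SAP 4.1.7.2). The required gap of at least 4 weeks puts such stops essentially before the screening window.
- **PK exclusions or deviations.** SAP 3.2.2 and 4.1.3.1 rest these on a data review meeting and a deviation plan. Neither section refers to imputed stop dates.
- **Disallowed use for the whole treatment period.** The SAP does not say how the disallowed label is assigned. After the Cycle 2 Day 1 PK assessment, the protocol provides for unavoidable CYP3A4 or CYP2C19 inhibitor use with a dose reduction.
- **Lost treatment-emergent events through the rule for a wholly missing start date.** That rule reads "Impute the first dose date unless the end date suggests it could have started prior to this". It could be taken to date events before first dose whenever an earlier start is conceivable, but its natural meaning is an end date before first dose. A literal reading would make the exception apply to nearly every recorded end date.

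**Conclusion.** The rule is wrong as written, and the consequence is confined to the medication tables. A drug stopped before first dose, with only the day unknown and with a calendar month equal to the last-dose month, is classed as concomitant instead of prior. It could then enter the allowed or disallowed table.

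The 92% applies only to day-missing screening stops in a month before the first-dose month, and only when the last dose is on day 700. It does not carry over to early discontinuation, to treatment continued beyond 25 cycles, or to children still on treatment at DCO1; the exposure is therefore mainly at DCO2 and DCO3. The 1-in-12 figure assumes that stop month and last-dose month are unrelated. The absolute number of misclassified records cannot be estimated, because the documents do not say how many partial stop dates exist.

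No primary or secondary endpoint is affected. The effect on adverse events is negligible, because treatment emergence depends on the start date. Severity: minor.

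**What to change.** In SAP 3.3.6.1, in the end-date bullet for a missing day, require both the month and the year to equal those of the last dose of study intervention before the last dose date is imputed. This matches the start-date bullet. Keep month-end imputation in all other cases.

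The cost is one phrase in the SAP and one condition in the derivation code. No new data are needed, and true stops in the last-dose month are handled as before.
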